1 BACKGROUND AND RATIONALE

Many different aneuploidy screening and diagnostic testing options are available to patients based on gestational age, all with different risks and benefits. Cell-free DNA screening has improved sensitivity and specificity for common aneuploidies¹ but likely reduced detection of other chromosomal abnormalities.² However, traditional screening such as first trimester screening, which have poorer detection characteristics for common aneuploidies, may be more likely to identify pregnancies other, less common, chromosomal abnormalities.² Diagnostic testing choices include chorionic villus sampling and amniocentesis, both of which carry a low risk of pregnancy loss of approximately 1 in 455 to 1 in 900 respectively.³ Counseling on screening and testing options is recommended by the American College of Obstetrics and Gynecology for all women, ideally at the first prenatal visit.⁴ Additionally, recommendations by the American College of Medical Genetics emphasize the importance of appropriate pretest counseling for patients undergoing prenatal screening with cell-free DNA.⁵

This increasing number of screening modalities complicates prenatal counseling for prenatal care providers and can be difficult for patients to understand, especially patients with low health literacy.⁶ While many patients may be aware of trisomy 21, many have never heard of other aneuploidies and may be unfamiliar with the basic principles of genetic screening and prenatal aneuploidy detection.

Because low health literacy affects many women of reproductive age and because most obstetric providers have limited time in an initial prenatal visit to explain the rapidly expanding choice of tests, our aim was to develop a decision aid for aneuploidy screening and testing that could easily be used in various clinics and settings. Decision aids have been shown to improve patients' knowledge and decrease decisional conflict with health care decisions in healthcare settings,⁶ and in the field of obstetrics and gynecology.^{6,7} This is particularly true when decisions are complex and involve patient value assessment.⁶ A decision aid has been previously developed and tested to address aneuploidy screening,⁸ though an important new screening modality in cell-free DNA has become available since the development of this tool. We hypothesize that a computerized decision aid to review available aneuploidy screening and testing options would not be inferior to a counseling visit with a genetic counselor in increasing patient knowledge. The combination of the decision aid followed by a genetic counseling appointment would also be expected to decrease decisional conflict.

1.1 Description of Intervention

A decision aid incorporating all aneuploidy screening and diagnostic testing options available at the time of the study was developed with input from maternal fetal medicine physicians, a geneticist, and genetic counselors. This was designed within a tablet-based application. The decision aid was also translated into Spanish by a single translator and the translation reviewed by a second native Spanish speaker. The language was simplified to a 10th grade reading level on the Flesch-Kincaid scale. Completion of the decision aid takes approximately 20 minutes. Information surrounding patient age and gestational age are incorporated to guide the study participant toward available options.

2 STUDY OBJECTIVE

2.1 Primary Objective

The primary hypothesis of this study was that knowledge scores of women in group 2 following completion of the decision aid only would not be inferior to knowledge scores of women in group 1 following genetic counseling. A noninferiority limit of 1 question different on a 12 point questionnaire was selected as a clinically relevant difference.

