3 INVESTIGATIONAL PLAN

3.1 Study Design

This is an unblinded randomized controlled trial.

Women randomized to group 1 will meet with the genetic counselor as scheduled, then complete the knowledge and decisional conflict assessments. Women randomized to group 2 will self-administer the decision aid within the app, then complete the knowledge and decisional conflict assessments. Following this, they will meet with the genetic counselor as scheduled; following this appointment, they will again complete the same assessment. Additionally, prior to and following meeting with the genetic counselor, women in group 2 will be asked whether they would or did find it helpful to meet with a genetic counselor.

Genetic counselors will be educated prior to study initiation that their counseling should not be modified based on group assignment; generally, women < 35 years old received abbreviated counseling on aneuploidy screening and testing options and those \geq 35 years old received more extensive counseling. Within ACMG guidelines, all screening tests are available to all women; cost information and insurance coverage information on available tests will also be provided prior to final decision making. Women will then undergo their screening or testing modality of choice. All study participation and completion of initial screening will be completed within the single encounter.

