4.3 Subject Completion/ Withdrawal procedures

Participants are instructed to inform their enrolling research study personnel should they desire to withdraw and participation could be terminated at that time.

5 STUDY EVALUATIONS AND MEASUREMENTS (how measurements will be made)

- Demographic characteristics will be abstracted from questionnaires and medical chart
 - o Age
 - o Race/ethnicity
 - o Preferred language
 - o Parity
 - o Gestational age
 - o Site of enrollment
 - o Insurance status
 - o Employment status
 - o Education level
 - o History of genetic counseling in prior pregnancy
- Baseline knowledge assessment
 - o This will be assessed via the previously described modified MSSKQ questionnaire prior to intervention
- Knowledge and decisional conflict scores as described will be collected via self-administered questionnaires embedded within the application

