6 STATISTICAL CONSIDERATION

6.1 Sample size calculation

An initial power calculation was performed using historical data from the maternal serum screening questionnaire assuming a standard deviation of 3 questions; to achieve 80% power with a 2-tailed alpha of 0.05, 92 women would be needed in each arm. Assuming a 7.5% fall-out rate from women with nonviable pregnancies, 100 patients were required in each arm for a total enrollment of 200 women.

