6.2 Statistical Methods

Baseline demographics

- Mean age - Wilcoxon rank sum
- AMA as categorical variable - chi2
- Race/ethnicity - Fisher exact
- Mean GA - Wilcoxon rank sum
- GA<14 wks as categorical - chi2
- Insurance status - Fisher exact
- Employed yes/no - chi2
- Education level - fisher exact
- Religion - Fisher exact
- Prior GC - chi2
- Planning invasive testing - Fishers exact
- Mean knowledge score on enrollment - Wilcoxon rank sum

Results

1. Compare control group following genetic counseling to intervention group following decision aid
 - Mean knowledge - Wilcoxon rank sum
 - Mean decisional conflict - Wilcoxon rank sum
 - Planned test - Fisher exact

2. Compare control group following genetic counseling to intervention group following decision aid and genetic counseling
 - Mean knowledge - Wilcoxon rank sum
 1. Represented in figure
 - Decisional conflict - Wilcoxon rank sum
 1. Represented in figure
 - Planned test - Fisher exact
3. Compare intervention group following decision aid to intervention group following both decision aid and genetic counseling
 - Mean knowledge - Wilcoxon signed rank
 1. Represented in figure
 - Decisional conflict - Wilcoxon signed rank
 1. Represented in figure
 - Planned test - descriptive (% changed)

No interim analyses are planned.

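### The aim is noninferiority in raising knowledge, but no planned analysis compares scores with enrollment, so a noninferior result cannot show that either intervention raised knowledge

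*Combined protocol and SAP*

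**What the plan says.** The synopsis and Section 1 frame the question as one of raising knowledge: the aid "would not be inferior to a counseling visit with a genetic counselor in increasing patient knowledge". Section 2.1 turns this into a comparison of scores after the interventions: "knowledge scores of women in group 2 following completion of the decision aid only would not be inferior to knowledge scores of women in group" (here the control group, once its members have seen the counselor). It adds: "A noninferiority limit of 1 question different on a 12 point questionnaire was selected as a clinically relevant difference". The limit is not related to any expected effect of counseling.

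The first item under Results 1 in Section 6.2 is "Mean knowledge - Wilcoxon rank sum", for group 1 after counseling against group 2 after the aid. The synopsis adds a graphical assessment.

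Knowledge at enrollment is measured in all women (Section 4.2). Section 5 says of it: "This will be assessed via the previously described modified MSSKQ questionnaire prior to intervention". In Section 6.2 the enrollment score appears once, as a between-arm item in the baseline table. The only within-woman comparison is Results 3: group 2 after the aid against the same women after aid plus counseling.

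**The concern.** A claim of noninferiority in raising knowledge says something useful about the aid only if the comparator raised knowledge, and by more than the margin. If counseling adds less than 1 question out of 12, an aid that teaches nothing is truly within the limit. The trial could then report noninferiority when neither intervention had changed what women know.

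The documents state no expected gain from counseling. The evidence cited in Section 1 for improved knowledge concerns decision aids, not genetic counseling. The synopsis describes the comparator as an abbreviated visit. Section 3.1 says that women under 35 generally "received abbreviated counseling on aneuploidy screening and testing options". At stake is whether the primary conclusion can answer the question as the synopsis and Section 1 pose it.

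**Working it through.** **Inputs from the documents.** Margin 1 question (Section 2.1). From Section 6.1: "assuming a standard deviation of 3 questions", and "to achieve 80% power with a 2-tailed alpha of 0.05, 92 women would be needed in each arm".

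**Assumptions not in the documents.** Noninferiority is declared when the lower limit of the two-sided 95% CI for group 2 minus group 1 is above -1. Counseling's true gain over enrollment, g, is varied from 0 to 1.5 questions. The correlation r between enrollment and post-intervention scores is varied from 0.3 to 0.7, with SD 3 at both times.

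**The plan's own figure.** n per arm = 2 × SD² × (1.96 + 0.8416)² / margin² = 2 × 9 × 7.849 / 1 = 141.3, so 142. The stated 92 does not follow from margin 1 and SD 3. With SD 3 it corresponds to a difference of 3 × 2.8016 × √(2/92) = 1.24. The step to 100 does reproduce: 92 / 0.925 = 99.5, rounded up. The mismatch is a separate matter, and 92 is used below as the planned evaluable number.

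**Chance that an aid with zero effect meets the limit.** SE = 3 × √(2/92) = 0.442. The true difference is -g, so the probability is Φ((1 − g)/0.442 − 1.96).

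| Counseling's true gain g | (1 − g)/SE | Probability |
|---|---|---|
| 0 | 2.26 | 62% |
| 0.25 | 1.70 | 40% |
| 0.5 | 1.13 | 20% |
| 0.75 | 0.57 | 8% |
| 1.0 | 0 | 2.5% |
| 1.5 | -1.13 | 0.1% |

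With a smaller SD of 2.4 the first five values are 81%, 56%, 29%, 10.5% and 2.5%. The pattern is the same: the issue matters only where counseling adds less than about 1 question.

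**Precision of the missing quantity.** The 95% half-width for group 1's paired gain is 1.96 × 3 × √(2(1 − r)) / √92. This is 0.73, 0.61 and 0.47 question for r = 0.3, 0.5 and 0.7.

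**Does Results 3 fill the gap?** If the aid taught nothing and counseling taught much, group 2's score should rise after counseling, and Results 3 would show it. If the score does not rise, either the aid had already taught what counseling would have added, or neither taught anything. Results 3 does not refer to enrollment and so cannot tell these apart.

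**The case against.** Several points on the other side have force.

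- **The hypothesis as written is about post-intervention scores.** A reader might infer that the trial carries a false-positive rate of up to 62%. The documents do not support that. Section 2.1 calls 1 question a clinically relevant difference, so a true deficit below 1 question is noninferior as defined. The 62% at g = 0 is simply the power at a true difference of zero. At g of 1 or more, an inert aid passes at most 2.5% of the time.
- **Randomization.** The between-arm difference in post-intervention scores also estimates the difference in gains, so the comparison is not biased. It still does not show that either arm improved.
- **Size of the counseling effect.** A reader might infer that counseling is expected to do little. The documents do not establish this. Women aged 35 and over generally received fuller counseling (Section 3.1), and Section 1 describes many patients as unfamiliar with the subject, which leaves room to gain.
- **Existing information.** Saying that the plan offers nothing would be too strong. Arm means at enrollment and after the intervention will both be available and can be subtracted, and Results 3 is a partial signal. But no gain, interval or interpretation is prespecified.
- **Repeat testing.** Both questionnaires fall within one visit and there is no uncounseled arm, so a pre-post gain mixes counseling with retest effects. This stands, and it limits what the added analysis can prove.

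**Conclusion.** The point holds as a gap between the stated aim and the analysis. The aim is noninferiority in raising knowledge, while the planned analyses cannot separate an aid and counseling that both worked from an aid and counseling that both did nothing. The test of the Section 2.1 hypothesis is not thereby invalid.

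The size of the problem depends on a gain that the documents do not give. Under the assumed interval rule, with SD 3 and 92 per arm, the chance that an inert aid meets the limit runs from 62% if counseling adds nothing to 2.5% if it adds 1 question. If counseling adds clearly more than 1 question, the concern has little practical effect, and the added analysis would support the conclusion.

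**What to change.** In Section 6.2, Results 1, prespecify the paired gain in knowledge (post-intervention minus enrollment) with a 95% CI in each arm: group 1 after counseling, group 2 after the aid.

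In Section 2.1, state that the noninferiority result will be read beside group 1's gain and the 1-question limit. Word the conclusion as noninferior in increasing knowledge only if knowledge rose from enrollment, and say in advance what counts as a rise. Otherwise, or if group 1's gain is below about 1 question, report that post-intervention scores were similar but that the margin was not informative about the aid's effect.

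Group 1's lower confidence limit should not have to exceed 1 as a pass/fail condition. For an aid truly equal to counseling and a true gain of 1.5 questions, the chance of meeting both that condition and the noninferiority limit would be 11%, 17% and 29% for r = 0.3, 0.5 and 0.7, against 62% for the noninferiority limit alone. That would often block a sound claim.

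The cost is one more table row from data already collected, a few lines of text, and possibly a more cautious conclusion. The report should state that the gain includes repeat-testing effects.

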2.2 Secondary Objective

Secondary outcomes included decisional conflict following decision aid completion, decisional conflict following decision aid completion and genetic counseling, change in knowledge score after genetic counseling in women who used the decision aid, choice of testing, and pursuit of invasive testing with high risk results.

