4.2 Intervention

Following informed consent, the app was accessed and a study ID assigned. Via a coin-flip algorithm within the app, women were randomly assigned to group 1 (control group) or group 2 (decision aid group). As it was not pragmatic for this study, randomization assignment was not blinded. Investigators were not involved in developing the randomization scheme within the app. All women completed an initial demographic and knowledge questionnaire immediately following randomization via self-administered assessments within the app.

Study flow is described in the below figure. Women randomized to group 1 met with the genetic counselor as scheduled, then completed the knowledge and decisional conflict assessments. Women randomized to group 2 self-administered the decision aid within the app, then completed the knowledge and decisional conflict assessments. Following this, they met with the genetic counselor as scheduled; following this appointment, they again completed the same assessment.

Additionally, prior to and following meeting with the genetic counselor, women in group 2 were asked whether they would or did find it helpful to meet with a genetic counselor.

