7 DATA COLLECTION AND MANAGMENT

Results to questionnaires are stored within the study application and will be downloaded onto a secure server by study personnel following each study visit. These files will be encrypted and password protected. This data will then be transferred into REDCap data management system for storage and access for statistical analysis by the primary investigator.

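### Does the secondary outcome on invasive testing after a high-risk result lack a measurement and an analysis in a way that requires a change to the plan?

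*Combined protocol and SAP*

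**What the plan says.** All references are to the combined protocol and SAP.

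- **Section 2.2** names five secondary outcomes: decisional conflict after the aid, decisional conflict after the aid plus counseling, change in knowledge after counseling among aid users, choice of testing, and "pursuit of invasive testing with high risk results". The last is separate from choice of testing and is not defined further. The synopsis objectives mention the test chosen but not this outcome.
- **Synopsis, 3.1 and 3.3** confine each woman's participation, including her initial screening, to one visit with no follow-up. **Section 3.4** excludes women already screened in this pregnancy.
- **Section 4.2** places the first questionnaire before either arm receives anything: "All women completed an initial demographic and knowledge questionnaire immediately following randomization".
- **Section 5** has demographic characteristics taken from questionnaires and the chart, and then states: "Knowledge and decisional conflict scores as described will be collected via self-administered questionnaires embedded within the application".
- **Section 6.2** lists "Planning invasive testing - Fishers exact" among the baseline characteristics, in the same block as "Mean knowledge score on enrollment - Wilcoxon rank sum". Its results comparisons cover knowledge, decisional conflict and planned test, the last entered between groups as "Planned test - Fisher exact".
- **Section 7** describes the data flow for questionnaires: "Results to questionnaires are stored within the study application".

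**The concern.** A reader who follows this outcome through the plan finds no landing place for it.

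If it means uptake of an invasive test after a positive screen, the result would ordinarily arrive after the visit. That timing is an assumption, since the plan gives no turnaround time. Participation ends at the visit, and the data sections name neither screening results nor later procedures.

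If it means intention, the only matching analysis line is a baseline one. A comparison on an item asked before the intervention cannot show an effect of the aid.

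The two readings differ in population, time point and analysis. In principle, the one reported as the listed outcome could be picked once the data are in hand.

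**Working it through.** **Step 1. Match outcomes to results lines (2.2 against 6.2).**

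| Secondary outcome | Results line in 6.2 |
|---|---|
| Decisional conflict after the aid | Comparison 1 |
| Decisional conflict after aid and counseling | Comparison 2 |
| Knowledge change after counseling, aid users | Comparison 3 |
| Choice of testing | Planned test, comparisons 1 to 3 |
| Invasive testing with a high-risk result | None |

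Four of five are covered. The gap is real.

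**Step 2. Is the meaning really open?** The outcome is conditional on a high-risk result. Nobody enters with one, because prior screening is an exclusion, so the plain meaning is what women did once a result was known. An intention reading needs a hypothetical question about a future positive screen, which no section describes. Stated plans are already covered by choice of testing. The baseline line "Planning invasive testing - Fishers exact" is not conditional on a result, and nothing in the plan says it measures this outcome.

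**Step 3. Is measurement ruled out?** No. The single-visit statements limit the woman's participation, and 3.1 speaks only of initial screening. They do not exclude chart review. Staff read charts for eligibility (4.1) and for demographics (5). Section 5 is also not an exhaustive list: planned test and religion are both analyzed in 6.2, and the helpfulness question to group 2 is described in 3.1 and 4.2, yet section 5 lists none of them. Its silence is weak evidence that an item was not collected. The questionnaire items and the study-flow figure are not available to check.

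**Step 4. How many women are concerned?** Inputs: 92 evaluable women per arm, 184 in all (6.1). Assumed, because the plan gives neither: a high-risk rate of 2% to 5% among screened women, and 60% to 100% choosing screening.

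Expected number = 184 × share screened × high-risk rate:

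- lowest: 184 × 0.60 × 0.02 = 2.2 (1.1 per arm)
- highest: 184 × 1.00 × 0.05 = 9.2 (4.6 per arm)
- at a 10% rate with all screened: 184 × 0.10 = 18.4 (9.2 per arm)

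Chance that at least one arm has no such woman = 1 − [1 − (1 − q)^92]², where q = share screened × rate:

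- q = 0.012: 0.988^92 = 0.329, giving 1 − 0.671² = 0.55
- q = 0.020: 0.287
- q = 0.050: 0.95^92 = 0.0089, giving 1 − 0.9911² = 0.018

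**Step 5. Would the choice of analysis matter?** Take 5 such women per arm, just above the upper end of the 2% to 5% range, with 5 of the 10 having the procedure. The two-sided Fisher p-value is 2/252 = 0.008 for a complete split (5 of 5 against 0 of 5), but 2 × (25 + 1)/252 = 0.21 for 4 of 5 against 1 of 5. With 3 per arm, even a complete split gives 2/20 = 0.10. A test can say almost nothing here. The subgroup is also formed after randomization, through the test chosen and its result, so it is not a clean randomized comparison. Counts by arm are what the data can support.

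**The case for a change.** The strongest case for a change is that it does not depend on the ambiguity. Grant that uptake is meant: the plan still gives no data source, window, definition of high risk or results line. An item hidden in the app would not supply the missing line in 6.2. Planned test does not stand in for it, since choice of testing is listed separately and is not conditional on a result. Unplanned chart data may also be collected unevenly or lost, and the repair would be cheap.

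The textual part of this stands: the definition, the source and the analysis are unwritten. Whether consent covers later chart review cannot be judged from the available text.

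The claimed harm is much weaker. The bias from using a pre-intervention item arises only if an analyst takes an unconditional baseline characteristic and reports it as the conditional outcome, which the plan does not propose. The freedom to choose after seeing the data is narrow once the plain reading is adopted. It comes down to the window and the cut-off for high risk, applied to a handful of women. The natural choices are the laboratory's own classification and whatever invasive procedure the chart records afterwards, handled alike in both arms.

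**Conclusion.** No change is needed. The plan leaves the details of one minor secondary outcome unwritten, and competent analysts would fill them in the same way: uptake among women whose screen was reported as high risk, taken from the chart and shown as counts by arm after all counseling is complete. No stated rule or figure produces a wrong result. The primary knowledge comparison, the sample size and the other four secondary outcomes do not depend on this item.

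The size is about 2 to 9 women of 184 under the assumed 2% to 5% rate and 60% to 100% screening share, and about 18 at a 10% rate with all women screened. The conclusion rests on the plain reading of 2.2 as uptake and on charts being open to staff who already use them. It would weaken if the trial report presented the baseline planning item as this outcome, or drew an inferential claim from these few women.
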